2.0 STUDY OBJECTIVES

The objective of the currently proposed study is to provide pilot data for this longer-term research program. In preparation for this K23 application, we must achieve the following aims.

Aim 1: Determine the cross-sectional prevalence of undiagnosed and uncontrolled hypertension within the Cedars-Sinai Health System, as well as the patient, physician, and clinic characteristics associated with these outcomes. This will document the presence and extent of problems at this institution and reveal which populations and settings are most affected, providing insights that can be used to develop and implement future interventions.

Aim 2: Develop and pilot test new time-to-care and time-to-control measures. These measures will evaluate (1) how long it takes from when evidence exists in the EMR that patients meet criteria for hypertension before clinicians document a diagnosis and initiate treatment, (2) how long evidence exists that control is suboptimal before clinicians intensify treatment, and (3) how long each of these conditions exists before goal blood pressures are achieved. We plan to use these new measures in our future work because we expect them to be more responsive to changes in care than cross-sectional measures of control would be, and because they include both care processes (i.e., did clinicians do the right things) and outcomes (i.e., were clinical goals achieved), making it possible to distinguish whether suboptimal control is due lack of recognition, lack of action (e.g., clinical inertia), or insufficient action (e.g., suboptimal adjustment of antihypertensive medications).

Aims 3A and 3B: Aim 3A – Assess the validity, responsiveness, and potential utility of the new time-to-care and time-to-control measures. To assess validity, we can examine whether performance on the new measures is associated with performance on cross-sectional measures of blood pressure control. To assess responsiveness and potential utility, we can examine how performance changes with clinical practice. For example, the introduction of the 2017 ACC/AHA guidelines represented a marked change in the standard of care for hypertension in terms of criteria for diagnosis and blood pressure goals. If the

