4.0 STUDY DESIGN AND METHODS

Achieving these objectives and aims will involve an analysis of existing data from ambulatory care visits at clinics affiliated with Cedars-Sinai Medical Center from January 1, 2014 through March 30, 2019. Via a detailed study protocol, we will establish patient eligibility criteria, specify study variables and measures for extraction from the EMR, and specify descriptive and multivariate regression analyses

related to Aims 1-3. An Advisory Board consisting of local and national experts in EMR systems, population health, hypertension, and the implementation of quality improvement interventions will provide guidance and feedback on the protocol and after we have obtained preliminary data.

Patients will need to have at least two years of data available in CS-Link to be included in the study (defined as two or more clinic visits at least two years apart and occurring within the study dates). We will include ambulatory care visits with faculty, medical delivery network, and private physicians in all specialties if they use CS-Link. We will exclude care in the emergency department, urgent care, and hospital settings because blood pressure may be temporarily elevated due to acute illness. For eligible visits, we will obtain the recorded blood pressure values, whether the blood pressure was assessed manually or automatically (if available), and the physician identity (coded).

We will define blood pressure control based on the 2017 ACC/AHA guidelines (blood pressure <130/80). In sensitivity analyses, we will also consider control based on the JNC-7 guidelines (blood pressure <140/90), due to the recent change in the standard of care.

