We will create three time-to-care measures: time-to-diagnosis, for patients who qualify for new diagnoses; time-to-initiate, for the same patients; and time-to-intensify, for patients with established diagnoses. We will create two time-to-control measures, one for patients with new and one for patients with established diagnoses. The new time-to-care and time-to-control measures will be based on the 2017 ACC/AHA guidelines. We will define undiagnosed hypertension as two ambulatory blood pressures \geq 130/80 without an ICD-9/10 code for hypertension in the preceding year; uncontrolled hypertension will be defined using the same blood pressure criterion but patients will have an ICD-9/10 code for hypertension. A new diagnosis of hypertension will be defined as an ICD-9/10 code for hypertension without a prior code or antihypertensive medication use in the preceding year. We will define treatment initiation as the first prescription for an antihypertensive medication following a new diagnosis of hypertension. Treatment intensification will represent the addition of another antihypertensive medication, an increase in the dose of an existing antihypertensive medication, and a change from one antihypertensive medication to another. We will access the 2017 guidelines and other standard sources to develop a list of antihypertensive medications. Time to care will be calculated as the number of days from the last blood pressure above goal to the documentation of the diagnosis or the initiation/intensification of treatment. Time to control will be calculated as the number of days from the last blood pressure above goal to the first blood pressure at goal.

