7.0 STATISTICAL CONSIDERATIONS

7.1 STUDY OUTCOME MEASURES

Analyses will test the following pre-specified hypotheses for each goal:

Aim	Hypotheses
1: Determine cross-sectional prevalence of undiagnosed and uncontrolled hypertension at CSMC, as well as the patient, physician, and clinic characteristics associated with these outcomes.	
 1) Cross-sectional rates of undiagnosed and uncontrolled hypertension at CSMC, based on the 2017 AA/AHA Guidelines, will be similar to national rates (20% and 50%, respectively). 2) Cross-sectional rates of undiagnosed and uncontrolled hypertension will be higher under the 2017 ACC/AHA Guidelines than the JNC-7 Guidelines. 3) Rates of undiagnosed and uncontrolled hypertension will be lower among patients with visits in Primary Care, Internal Medicine, Nephrology, or Cardiology clinics than for patients who only receive care in other clinics.
2: Develop and pilot test new time-to-care and time-to-control measures.	
 1) Data already collected in the EMR can be used to calculate these five new measures of hypertension care.
3A: Assess the validity, responsiveness, and potential utility of the new time-to-care and time-to-control measures.	
 1) Performance on the time-to-care and time-to-control measures will be associated with cross-sectional control rates at the clinic and physician level. 2) Following release of the 2017 ACC/AHA Hypertension Guidelines, performance on the time-to-control measures and cross-sectional control rates will worsen while performance on time-to-care measures will remain stable. 3) Performance on the time-to-care and time-to-control measures will be better for patients with visits in Primary Care, Internal Medicine, Nephrology, and Cardiology clinics than for patients who only receive care in other clinics.

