For Aim 3A, we will conduct unadjusted and then adjusted multivariate regression analyses assessing whether time-to-care and time-to-control measures are predictors of (i.e., associated with) blood pressure control rates at the physician level. We will perform these analyses at the physician and clinic levels because time-to-control rates are tautologically associated with the presence of control, and because many types of future quality improvement interventions would likely target individual physicians and clinics. We will compare performance on these measures and control rates between patients with visits in Primary Care, Internal Medicine, Nephrology, and Cardiology clinics than for patients who only receive care in other specialty and subspecialty clinics.

Next, we will perform interrupted time-series analyses of changes in the three hypertension measures after 2017 using multivariate regression models. These analyses will examine each hypertension measure (time-to-care, time-to-control, and control rates) as the dependent variable, using the quarter year as the independent variable. We will examine whether there is a change in intercept or slope during any quarter following the announcement of the ACC/AHA guidelines in 2017. We will then qualitatively compare such changes across the three outcome measures, to assess whether time-to-care is more responsive, as expected.

For Aim 3B, we will conduct unadjusted and then adjusted multivariate regression analyses assessing whether time-to-control measure was different between those enrolled in the pilot study and patients in the non-intervention group.

For Aim 4A, two independent coders will develop a codebook that details the inclusion and exclusion criteria, as well as typical exemplars for each topic or theme. Together, the coders will work to establish inter-coder reliability (evidenced by Cronbach's alpha $\geq .70$) with the goal to converge on a single, agreed upon meaning for each thematic area. For each topic, they will identify the range of themes mentioned, which were most and least salient, and which were discussed most and least frequently. This will produce research reports on specific topics describing the range, central tendency, and distribution of each theme, presenting segments of text as exemplars, which will be used to guide the refinement and implementation of the intervention in Aim 4B.

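### Aim 3A judges whether time-to-care is the more responsive measure by eye across three separate models, with no common scale, contrast or interval, and its expected result conflicts with the plan's own hypothesis

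*Protocol*

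**What the plan says.** Protocol 7.1 (Aim 3A) plans interrupted time-series regressions that take "each hypertension measure (time-to-care, time-to-control, and control rates) as the dependent variable, using the quarter year as the independent variable". On what counts as a change it says: "We will examine whether there is a change in intercept or slope during any quarter following the announcement of the ACC/AHA guidelines in 2017". The results are then set side by side: "We will then qualitatively compare such changes across the three outcome measures, to assess whether time-to-care is more responsive, as expected".

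The units come from Protocol 4.0. For the first measure, "Time to care will be calculated as the number of days from the last blood pressure above goal to the documentation" of a diagnosis or of treatment being started or stepped up. For the second, "Time to control will be calculated as the number of days from the last blood pressure above goal" to the first reading at goal. Control is a reading below 130/80, so the control rate is a proportion.

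Two other places bear on the expected result. Protocol 2.0 (Aim 2) supports later use of the new measures because "we expect them to be more responsive to changes in care than cross-sectional measures of control would be". The hypothesis table in 7.1 predicts that after the 2017 guidelines "performance on the time-to-control measures and cross-sectional control rates will worsen while performance on time-to-care measures will remain stable".

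The SAP deals only with the adherence trial and adds nothing on Aim 3A.

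**The concern.** A claim that one measure responds more than another concerns a difference between two responses. The plan estimates each response in its own model and never estimates the difference. Two of the three possible comparisons also set days against a proportion, where raw coefficients have no common meaning. Time-to-care against time-to-control is days against days, so there the gap is the missing contrast, not the unit.

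Allowing an intercept or slope change in any later quarter gives each measure several chances to show a change, with no rule for multiplicity. The stated expectations also point in different directions.

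At stake is one of the two reasons that Protocol 2.0 gives for carrying the new measures into later research (the other is that they cover both care processes and outcomes). This step is the only planned comparison of how the different measures respond to a change in care. The comparison across clinic types in 7.1 does not concern change over time, and Aim 3B looks at time-to-control alone.

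**Working it through.** **No figure to reproduce.** Protocol 7.2 supports Aim 3A by data volume only (at least 75,000 patients, over 2.5 million readings). No alpha, power, effect size, SD or correlation is stated.

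**Inputs from the documents.** Data end on 30 March 2019. A 2012 start (Protocol 3.2, 5.2) gives 7 × 4 + 1 = 29 quarters; a 2014 start (Protocol 4.0) gives 5 × 4 + 1 = 21. Quarters after 2017: 4 + 1 = 5.

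**Assumptions.** Measures are called different when one shows a significant change and another does not. Tests are two-sided at 5% per coefficient. Every measure has the same standardised level shift, from 0 to 4 quarterly residual SDs. Correlation between measures is 0, 0.5 or 0.8, with no autocorrelation.

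**Step 1: independent measures, each flagged with probability p.**

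- A given pair disagrees: 2p(1−p).
- Some disagreement among three: 1 − p³ − (1−p)³ = 3p(1−p).
- Time-to-care flagged and control rate not: p(1−p).

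| p | Pair | Among three | Time-to-care flagged, control rate not |
|---|---|---|---|
| 0.30 | 42% | 63% | 21% |
| 0.50 | 50% | 75% | 25% |
| 0.70 | 42% | 63% | 21% |
| 0.80 | 32% | 48% | 16% |
| 0.95 | 10% | 14% | 5% |

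A pair never exceeds 50%. Three-way disagreement exceeds 50% only if p(1−p) > 1/6, that is, for p between about 0.21 and 0.79.

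**Step 2: segmented-regression simulation.** There were 20,000 runs per setting, with 5 post-guideline quarters. A measure is flagged if its intercept or slope change is significant.

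| Setting | Each measure flagged | Pair, correlation 0 / 0.5 / 0.8 | Among three, correlation 0 / 0.5 / 0.8 |
|---|---|---|---|
| One breakpoint, 2-SD shift, 21 quarters | 55% | 50 / 36 / 23% | 74 / 54 / 35% |
| One breakpoint, 2-SD shift, 29 quarters | 61% | 48 / 34 / 22% | 72 / 52 / 33% |
| One breakpoint, 4-SD shift, 21 quarters | 98% | 3 / 3 / 2% | 5 / 4 / 3% |
| Any quarter, no true change, 21 quarters | 26–27% | 39 / 34 / 24% | 59 / 50 / 36% |
| Any quarter, no true change, 29 quarters | 26% | 39 / 33 / 23% | 58 / 50 / 35% |

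With no response at all, searching every post-guideline quarter flags each measure about 26% of the time, against 8–9% with one breakpoint.

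**Step 3: the stated expectations side by side.** The analysis text in 7.1 expects time-to-care to respond more. The hypothesis table in 7.1 expects it not to move while the other two worsen. Protocol 2.0 (Aim 3A) gives the same stable pattern, on the condition that clinicians are recognising raised pressure and acting on it. If time-to-care moves most, the first text is met; if it stays flat, the second is.

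**Step 4: does a formal contrast behave?** With one breakpoint and a standardising unit fixed in advance, two equally responsive measures are declared different in 4.7–5.2% of runs. If the unit is each series' estimated pre-period SD and its uncertainty is ignored, this becomes 5.4–6.3% with no shift and 11–20% at a 4-SD shift. The interval must therefore carry the SD's uncertainty.

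**The case against.** The plan says only that the comparison is qualitative. It names no significance split and no ranking by raw size, so any error rate rests on a rule supplied by the reader. The measures come from the same patients, and 7.1 itself notes that time-to-control is bound up with control, so independence overstates disagreement. With this volume of data, power may be high and disagreement rare. Aim 3A is retrospective pilot work, and a qualitative look at direction suits the predicted pattern of two measures worsening and one staying flat.

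Much of this stands, and it rules out two stronger readings:

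- A reader might infer that equally responsive measures would usually be declared different. The documents do not support that. Even under the assumed split a pair disagrees at most half the time, and three-way disagreement passes half only at intermediate power with low to moderate correlation.
- A reader might infer that a measure in days must always outrank a proportion. No such rule appears, and the ranking depends on the unit. With assumed SDs of 100 days and 0.5, a 0.3-SD change is 30 days against 0.15, but also about 1 month against 15 percentage points.

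The central gap remains. Under any informal rule the difference in responsiveness is never estimated. Reading the step as a check of pattern does not rescue it: a flat time-to-care series would not show greater responsiveness, and a non-significant change does not show stability unless a margin is stated.

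**Conclusion.** The concern holds in limited form. As written, Aim 3A cannot support or refute the claim that time-to-care is more responsive, and the two statements of the expected result in 7.1 conflict. These conclusions need no assumption beyond the text.

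The size is conditional. Under an assumed significance split, false differences between equally responsive measures reach at most about 50% for a pair and about 75% somewhere among three. At a 2-SD shift with 21 quarters and correlation 0.8 they are 23% and 35%; at a 4-SD shift with one breakpoint they are 1–5%. The decision rule, alpha, effect sizes, correlations and absence of autocorrelation are all assumptions.

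The change should be made before the measures are put forward as more responsive in later work. It does not affect the randomised comparison in Aim 4B.

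**What to change.** In Protocol 7.1:

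1. Reconcile the expected direction for time-to-care with the hypothesis table and with Protocol 2.0. If stability is the prediction, state the margin within which a change counts as stable.
2. Name one breakpoint, the guideline announcement, in place of any later quarter. Say which of the time-to-care and time-to-control measures defined in 4.0 enter, and which start date (2012 or 2014) applies.
3. Express each measure's post-guideline change in units of its own pre-guideline residual SD around the fitted pre-period trend. A raw pre-period SD would absorb any existing trend and make a trending measure look less responsive.
4. Estimate two differences in absolute standardised change: time-to-care minus control rate, and time-to-control minus control rate. Give each a 95% interval from a joint model, or from a bootstrap that recomputes all three measures and their SDs together and allows for shocks common to a quarter. Resampling clinics or physicians alone would miss those shocks.
5. Claim greater responsiveness only if the interval lies wholly above zero. Merely excluding zero is not enough, since an interval wholly below zero would mean the opposite.

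The cost is a few sentences and somewhat more analysis of data already extracted. With about five post-guideline quarters the result may be inconclusive, and should then be reported so.

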7. Steps 5-7 will be continued for a total 8 weeks (ending 9 weeks after the in-person appointment). At that time, the clinical pharmacist will remind the patient at the end of their final phone call that they will no longer be reviewing their blood pressure or titrating their medications.
8. If at any time during the study, a patient's blood pressure is considered out of range (SBP<90 and patient symptomatic; DBP<40 and patient symptomatic; SBP>190 or DBP>115, regardless of symptoms), if the patient develops symptoms consistent with either significant hypotension or hypertension, has critical lab values (Na<125 or >150, K<3.0 or >5.5) or has any other concerning clinical finding, they will be instructed to seek care at the nearest Emergency Department.

Schedule of Procedures

Activity	In-Person Visit	Week 1	Week 2	Week 3	Week 4	Week 5	Week 6	Week 7	Week 8
Medical History/Exam	X								
Phone Call to Patient		X	X	X	X	X	X	X	X
Medication Titration	†	†	†	†	†	†	†	†	†
Laboratory Testing	†	†	†	†	†	†	†	†	†
Discharge from Study									X

X = Completed

† = Completed, as clinically indicated

Specific Protocols for Aims 4A and 4B Only:

We will also conduct interview discussions and a pilot RCT study of the use of text messaging and incentives to increase blood pressure medication adherence. Interview discussions will include 20 randomly selected patients currently taking hypertension medication and 7 clinic staff who have been employed for at least 12 months. We will conduct eight 1-hour interviews with patients recruited on a regular clinic day and one interview with providers & clinic staff to inform the intervention content (total of 27 participants). Open-ended questions will be asked before more closed-ended, probing questions so as not to bias responses and allow for exploring new leads and related topics, and to generate rich narratives. Answers to such questions will indicate the areas most important to respondents—which may, or may not, conform to our expectations. Standard probes, such as verification and compare and contrast questions, will be used. Based on the standards set by the CSMC IRB, all patients will receive \$30, while the providers and clinic staff will not receive payment. Findings from the interview discussion will be used to inform the pilot study intervention in Aim 4B.

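### Aim 4A judges inter-coder reliability by Cronbach's alpha of at least .70, a lenient rule on a consistency index although the stated goal is agreement

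*Protocol*

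**What the plan says.** The Aim 4A analysis is described in Protocol section 7.1. It states that "two independent coders will develop a codebook" and then: "Together, the coders will work to establish inter-coder reliability". The criterion follows in the same sentence: reliability is "evidenced by Cronbach's alpha" of at least .70. The sentence ends by giving the purpose, "with the goal to converge on a single, agreed upon meaning for each thematic area".

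The planned output for each topic is described next: "they will identify the range of themes mentioned, which were most and least salient, and which were discussed most and least frequently". The resulting reports, "which will be used to guide the refinement and implementation of the intervention in Aim 4B", also give the central tendency and distribution of each theme. Section 4.0 says the interviews are held "to inform the intervention content (total of 27 participants"), that is, 20 patients and 7 staff.

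No other reliability or agreement statistic is named. The coding unit, the coding scale, the share of text to be double-coded and the way disagreements are resolved are not given. The SAP does not cover inter-coder reliability.

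**The concern.** The purpose in section 7.1 is agreement: two people giving the same text the same code with the same meaning. Cronbach's alpha is built only from variances and covariances. For two coders it describes the reliability of their combined score, not how often they make the same decision, and it is not corrected for chance agreement. A threshold that looks demanding on this scale can be modest on an agreement scale.

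This matters because theme frequency and distribution are planned outputs. If one coder applies a code much more often than the other, those outputs depend on whose coding is used, and the stated rule may not flag it. The themes then inform the messaging and implementation of Aim 4B.

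**Working it through.** The .70 is a chosen cut-off with no derivation in the documents, so there is nothing to reproduce. The check is what it implies.

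**Inputs.** From section 7.1: two coders, Cronbach's alpha, threshold .70. Assumed, because the documents do not say: the coding scale. Three scales are considered.

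**Formulas.** With coder variances v1 and v2 and covariance c:
- alpha = 2[1 − (v1 + v2)/(v1 + v2 + 2c)], which is 2r/(1 + r) when v1 = v2, where r is the inter-coder correlation.
- Cohen's kappa = (Po − Pe)/(1 − Pe), with Po the observed and Pe the chance agreement.

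**Correlation at the cut-off (equal variances).** r = .70/(2 − .70) = .70/1.30 = 0.538.

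**Present/absent codes, both coders applying the code equally often.** Here kappa equals r, so kappa is 0.538 at the cut-off. With prevalence p, the share of segments on which they disagree is 2p(1 − p)(1 − r):
- p = .50: .50 × .4615 = 23.1%
- p = .20: .32 × .4615 = 14.8%
- p = .10: .18 × .4615 = 8.3%

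**Present/absent codes, unequal frequency.** A codes 20% of segments; B codes 40%, including all of A's.
- v1 = .20 × .80 = .16; v2 = .40 × .60 = .24; c = .20 − .20 × .40 = .12
- alpha = 2[1 − .40/.64] = .75, a pass
- Po = .80; Pe = .08 + .48 = .56; kappa = .24/.44 = .545

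A table exactly at the cut-off: of 100 segments, 35 coded by both, 30 by A only, none by B only, 35 by neither.
- v1 = v2 = .65 × .35 = .2275; c = .35 − .2275 = .1225
- alpha = 2[1 − .455/.700] = .70
- Po = .70; Pe = .455; kappa = .245/.545 = .45

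**Ordinal ratings, such as salience.** A's ratings are spread evenly over 1 to 4, and B is always one point higher. A constant shift leaves variances and covariance unchanged, so alpha = 1.00. Exact agreement is 0%. Pe = 3 × .25 × .25 = .1875, so unweighted kappa = −.1875/.8125 = −.23.

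**Unordered categories.** In a simulated four-category coding with 53% agreement and kappa .37, alpha ranged from .21 to .75 depending only on which numbers were assigned to the categories. The same coding could fail or pass.

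**Conversion for the fix (present/absent, equal marginals).** alpha = 2 × kappa/(1 + kappa):
- kappa .60: 1.20/1.60 = .75
- kappa .70: 1.40/1.70 = .82
- kappa .80: 1.60/1.80 = .89

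**The case against.** The best defence is that the threshold does not act alone. The coders work from a codebook with inclusion and exclusion criteria and exemplars, they aim to converge on one meaning per theme, and the text ties no action to passing or failing. Alpha is offered as evidence within a consensus process. This stands as mitigation, but it does not make alpha a measure of agreement, and no rule for reaching consensus is given.

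Some stronger readings are tempting but not supported:
- *That alpha ignores differences in how often codes are applied.* With present/absent codes it does not. In the 20% versus 40% example the frequency difference is the only disagreement, and it lowers alpha from 1.00 to .75. Alpha under-penalises it. Only a constant shift on an ordinal or numeric scale is ignored altogether.
- *That coders who pass do not agree.* In the present/absent examples above, agreement is 70% or more and kappa is about .45 to .55. That is substantial disagreement, not its extreme.
- *That the themes determine Aim 4B.* Section 7.1 says they guide it and section 4.0 that they inform it. Section 4.0 already fixes the three arms, the daily texts, the 3-month period, the prize values and the 80% adherence rule. The hypothesis table in section 7.1 calls Aim 4A exploratory, and no Aim 4B outcome depends on alpha.

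A reader might also suppose that Krippendorff's alpha was meant. Nothing in the documents says so, and if it was, the text still needs correcting.

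**Conclusion.** The point holds. The protocol's only numerical criterion for inter-coder reliability is a consistency index, while its stated goal is agreement, and neither document supplies another criterion.

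The size depends on the coding scale. At the cut-off with present/absent codes and equal marginals, kappa is 0.54; with unequal marginals it can be about .45, with 30% disagreement. For ordinal ratings the rule can be met with no exact agreement, and for unordered categories alpha has no fixed meaning. The code frequencies and tables used here are illustrations, not figures from the documents.

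The practical impact is minor. What is at risk is the accuracy of theme frequencies and distributions that feed the refinement of the intervention, not the Aim 4B efficacy comparison.

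**What to change.** In Protocol section 7.1, replace Cronbach's alpha with a chance-corrected agreement coefficient suited to the coding scale:
- nominal or present/absent codes: Cohen's kappa or Krippendorff's alpha;
- ratings or counts: weighted kappa, or the ordinal or interval version of Krippendorff's alpha.

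Report it per theme against a stated threshold, computed on independently double-coded segments before consensus. State the coding unit and scale, the share of text double-coded, and how remaining disagreements are settled.

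The cost is a few sentences and the analysis of double-coded text; no new interviews are needed. There are two downsides. Keeping .70 as the number tightens the rule, since kappa .70 corresponds to an alpha of about .82 with equal marginals, so some themes may need another round of codebook refinement. And with 27 participants, per-theme estimates for rare themes will be imprecise, so the coefficient should be read together with raw agreement and the number of coded segments.
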